9.4.4 SAFETY ANALYSES

Safety Endpoints:

1. **Infection.** Patient's charts will be reviewed at the completion of their 3-month office visit follow-up in order to analyze if they visited the dermatologist between the date of surgery and 3-month office visit and if infection was diagnosed.

2. **Bleeding**. During each of the weekly follow-up questionnaires and during the 3-month follow-up visit, patients will be asked if they have experienced any post-operative bleeding that led to a visit to the physician (yes/no) and if there was any intervention performed by the physician to stop the bleeding (yes/no). Bleeding will be considered an adverse event if an intervention by a physician was required to stop the bleeding. The number and percentage of patients who experienced bleeding at any time during the 3-month follow-up period will be reported.

3. **Pain**. The proportion of patients with a pain score ≥ 6 at the operative site will be assessed at one week following surgery. This will be based on the patient's response to the weekly follow-up questionnaire, with scores ranging from 1 (no pain) to 10 (worst imaginable pain).

Statistical Analysis: We will report the frequency and proportion of patients experiencing each of the safety endpoints above, based on the Safety Population defined in Section 9.3. The proportion of patients experiencing each type of complication (infection, bleeding, pain) will be compared between porcine xenograft and second intention healing using Fisher's exact test.

In addition to the planned safety analysis at the completion of the study, one interim analysis will be conducted by the study statistician after 26 patients have been randomized and complete the final study visit at 3 months post-intervention. This is equal to approximately 50% of the planned enrollment goal of 50 patients. The purpose of this interim analysis will be to review the safety endpoints. There will be no formal stopping rule based on the statistical significance of the interim safety analysis. The principal investigator will alert the IRB immediately if there is any evidence or suggestion of a difference between treatment groups with regard to AEs or SAEs. Additional details on this interim safety analysis are included in Section 9.4.6.

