To compare complication rates following second intention healing or porcine xenograft dressing of surgical wounds on the lower extremities.	 Infection. Patient's charts will be reviewed at the completion of their 3-month office visit follow-up in order to analyze if they visited the dermatologist between the date of surgery and 3-month office visit and if infection was diagnosed. Bleeding. During each of the weekly follow-up questionnaires and during the 3-month follow-up visit, patients will be asked if they have experienced any post-operative bleeding that led to a visit to the 	To help keep the patients as safe as possible.
	physician (yes/no) and if there was any intervention performed by the physician to stop the bleeding (yes/no). The number and percentage of patients who experienced bleeding at any time during the 3-month follow-up period will be reported.	

OBJECTIVES	ENDPOINTS	JUSTIFICATION FOR ENDPOINTS
	3. Pain. The proportion of patients	
	with a pain score > 6 at the operative	
	site will be assessed at one week	
	following surgery. This will be based	
	on the patient's response to the	
	weekly follow-up questionnaire, with	
	scores ranging from 1 (no pain) to 10	
	(worst imaginable pain).	

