7.3 LOST TO FOLLOW-UP

If patients fail to show up for the follow-up visit, they will be withdrawn from the study. An evaluable patient will be one who completes the final 3 month follow -up office visit.

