8.3.4 TIME PERIOD AND FREQUENCY FOR EVENT ASSESSMENT AND FOLLOW-UP

The occurrence of an adverse event (AE) or serious adverse event (SAE) may come to the attention of study personnel during study visits and interviews of a study participant presenting for medical care, or upon review by a study monitor.

All AEs including local and systemic reactions not meeting the criteria for SAEs will be captured on the appropriate case report form (CRF). Information to be collected includes event description, time of onset, clinician's assessment of severity, relationship to study product (assessed only by those with the training and authority to make a diagnosis), and time of resolution/stabilization of the event. All AEs occurring while on study must be documented appropriately regardless of relationship. All AEs will be followed to adequate resolution.

Any medical condition that is present at the time that the participant is screened will be considered as baseline and not reported as an AE. However, if the study participant's condition deteriorates at any time during the study, it will be recorded as an AE.

Changes in the severity of an AE will be documented to allow an assessment of the duration of the event at each level of severity to be performed. AEs characterized as intermittent require documentation of onset and duration of each episode.

[name] will record all reportable events with start dates occurring any time after informed consent is obtained until 7 (for non-serious AEs) or 30 days (for SAEs) after the last day of study participation. At each study visit, the investigator will inquire about the occurrence of AE/SAEs since the last visit. Events will be followed for outcome information until resolution or stabilization.

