9.3 POPULATIONS FOR ANALYSES

A modified intention to treat analysis will be performed. All patients will be analyzed according to randomized treatment assignment, unless a patient prefers an alternative treatment method between the time he/she is randomized and the procedure (in which case the patient will be excluded from the study). The **Modified Intention-to-Treat (mITT) Population** will consist of all patients who receive the study intervention and show up for the 3-month office visit follow-up, during which the primary endpoint is evaluated. The Modified Intention-to Treat Population will also include patients who required the rescue therapy, and had the primary endpoint assessed at a follow-up visit when the wound had completely healed. This population will be used to analyze the primary endpoint and all secondary endpoints.

The **Safety Population** will consist of all patients who receive the randomized study intervention. This population will be used to analyze all safety endpoints.

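### The infection endpoint rests only on a chart review tied to the 3-month visit, so it can miss infections diagnosed elsewhere and has no rule for treated patients who miss that visit

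*Combined protocol and SAP*

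**What the plan says.** Section 9.4.4 and the Section 3 table give the same definition of infection. The timing is: "Patient's charts will be reviewed at the completion of their 3-month office visit follow-up". The reviewer then looks to see "if they visited the dermatologist between the date of surgery and 3-month office visit and if infection was diagnosed". No other source is named.

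Bleeding, the next endpoint in both lists, is collected differently: "During each of the weekly follow-up questionnaires and during the 3-month follow-up visit, patients will be asked if they have experienced any post-operative bleeding". That question concerns bleeding that led to a visit to a physician, without limiting it to dermatology. Section 8.1 runs the weekly questionnaires to 12 weeks.

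For the denominator, Section 9.3 says the Safety Population "will consist of all patients who receive the randomized study intervention", and adds: "This population will be used to analyze all safety endpoints". Section 9.4.4 repeats this: "We will report the frequency and proportion of patients experiencing each of the safety endpoints above, based on the Safety Population defined in Section 9.3". Attendance at 3 months is not required. Section 7.3 deals with non-attenders in these words: "If patients fail to show up for the follow-up visit, they will be withdrawn from the study".

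Separately, Section 4.1 has complications and adverse events recorded in both groups, and Section 8.3.4 states: "At each study visit, the investigator will inquire about the occurrence of AE/SAEs since the last visit".

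**The concern.** The numerator and the denominator come from different sets of patients. The numerator needs a completed 3-month visit, because that is what triggers the review, and a dermatologist's diagnosis. The denominator needs only that the patient was treated. No text says what happens to a treated patient for whom the review is never triggered, or to an infection diagnosed in primary care, urgent care or an emergency department.

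A lower infection rate is one of the benefits the background (Section 2.2) hopes for from xenograft, and comparing complication rates is a stated objective. The arms are compared on infection at the interim and final analyses. There is no formal stopping rule; the principal investigator is to alert the IRB to any sign that the arms differ on adverse events (Sections 9.4.4 and 9.4.6). With so few events expected, that judgement depends on individual cases, so a complete count matters more than the p-value.

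**Working it through.** **Inputs from the documents.** N = 50, 25 per arm, 10% attrition (Section 9.2); infection rate under 1% (Section 2.3.1); overall complication rate 1.6% (Section 8.3.2); Fisher's exact test (Section 9.4.4), two-sided at 0.05 (Section 9.4.1). The documents give no power figure for infection.

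**1. The plan's own N.** 38/0.864 = 43.98, so 44. 44/0.90 = 48.9, so 49, or 50 as an even 1:1 total. The plan's figure reproduces, and this point does not change it.

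**2. Patients with no trigger.** 10% of 50 = 5; if exactly 44 complete, 50 − 44 = 6. This reads attrition as treated patients who miss the visit. Section 9.2 does not define the term.

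**3. What the missing rule does to the reported rate.** Suppose no infection is recorded and every infection among attenders was captured.
- Possible true proportion in the 50: 0 to 5/50 = 10%, or 0 to 6/50 = 12%.
- One-sided 95% upper limit, 1 − 0.05^(1/n): 5.8% for 0/50; 6.4% for 0/45; 6.6% for 0/44.
- A single infection reads as 1/50 = 2.0%, 1/45 = 2.2% or 1/44 = 2.3%.

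**4. Outside diagnoses.** The documents do not give the share of infections diagnosed by another provider, so I assume 0%, 25% and 50%. I also assume that 10% miss the visit independently of infection and are counted as uninfected. Captured share = 0.90 × (1 − share elsewhere). Expected recorded infections in 50 = 50 × 0.01 × captured share.

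| Share elsewhere | Captured share | True 1% reads as | Expected recorded (true 0.5) |
|---|---|---|---|
| 0% | 90% | 0.90% | 0.45 |
| 25% | 67.5% | 0.68% | 0.34 |
| 50% | 45% | 0.45% | 0.23 |

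If the whole 1.6% complication rate were infections, the true expected count would be 50 × 0.016 = 0.8.

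**5. The Fisher test.** At 25 per arm, 5 against 0 gives p = 0.0502 and 6 against 0 gives p = 0.022, so six events against none are needed. Exact power, summing the binomial probabilities of all tables with p ≤ 0.05:

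| Assumed true rates | Full capture | 90% | 67.5% | 45% |
|---|---|---|---|---|
| 1% vs 10% | 2.8% | 1.8% | 0.5% | 0.1% |
| 1% vs 20% | 34% | 26% | 10% | 2% |

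Incomplete capture erodes power only for differences far beyond the documented rate. Near that rate there is almost no power to lose.

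**6. Chance that an arm of 25 shows no infection.** At a true 1%: 0.99^25 = 0.78 with full capture, and 0.995^25 = 0.88 with an assumed 50% capture.

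**The case against.** The best defence is the adverse event system. Section 4.1 records complications in both groups, Section 8.3.2 names postoperative infection among the events of dermatologic surgery, and Section 8.3.4 allows capture from visits, interviews and patients presenting for care. An infection treated elsewhere could be recorded there. That stands, and a reader should not infer that such infections are lost to the trial altogether. But nothing carries those records into the infection endpoint, and Section 9.4.6 sends the reader back to Section 9.4.4 for the definition. The inquiry at visits also depends largely on the 3-month visit, the only post-surgery visit scheduled for everyone in Section 1.3.

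Other points also stand in part:
- A chart may hold outside records, a non-attender's chart might still be reviewed, and Section 4.1 provides for calling back patients who miss appointments. The text neither arranges nor rules out the first two.
- Chart diagnosis may be a deliberate choice, since Section 3 calls complication rates objective endpoints. This argues for keeping confirmed cases visible, not for one source alone.
- The full questionnaire is not in the documents, so it can be said only that no infection item is described.
- The interim is timed to 26 patients who have completed the final visit, so the missed-visit gap bears mainly on the final analysis.
- The ±1 month window means the look-back can run from 2 to 4 months, but it applies to both arms and nothing suggests that visit timing differs by arm.

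**Conclusion.** The endpoint as written can under-count infections and leaves the status of treated non-attenders undefined. About 5 or 6 of 50 patients are affected at the planned attrition, plus an unknown number of outside diagnoses. The first figure rests on reading attrition as treated patients who miss the visit; the effect of outside diagnoses rests on the assumed shares above. This is a cheap improvement to safety reporting. It does not threaten the primary analysis or change the likely Fisher result.

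Three stronger readings are tempting but unsupported:
- **That these patients are scored as uninfected.** This is the likely default when the denominator is the whole Safety Population, but the plan does not say so; their status could equally be set to missing.
- **That the under-count favours one arm.** Patients know their allocation, so care-seeking could differ, but nothing in the documents shows that it does or in which direction.
- **That the chance of an arm showing no infections roughly doubles.** With an assumed 5% rate and 50% capture it rises from 0.95^25 = 28% to 0.975^25 = 53%. That rate is at least five times the documented one; at 1% the move is from 0.78 to 0.88.

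**What to change.** Amend Section 9.4.4 and the Section 3 table as follows:
1. Add one item to the weekly questionnaire and the 3-month visit, parallel to bleeding, asking whether any physician or clinic has diagnosed an infection of the surgical wound. Check each positive answer against records where possible.
2. Count as infection any such diagnosis found by chart review, adverse event record or patient report, and report record-confirmed cases separately. Do not count an antibiotic prescription alone, because Section 9.4.5 shows that prophylaxis after surgery is expected in some patients.
3. Review the chart of every Safety Population patient over one fixed window from surgery, for example 12 weeks to match the questionnaires, whether or not the 3-month visit was attended.
4. Report by arm how many patients have incomplete ascertainment, and state in advance how they enter the proportion.

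The cost is one question on an existing form, chart review for a handful of additional patients, and a few sentences in an amendment. Sample size and treatment are unchanged. The downside is that some self-reported infections from unblinded patients will remain unconfirmed, which is why the confirmed subset is shown separately.

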6.5.1 RESCUE MEDICINE

The study sites will supply the topical application of rescue medication that will be obtained locally. The following rescue medications may be used:

Silver Nitrate Wood Applicator Sticks Henry Schein Model: 1126994

The use of rescue medication is allowable after the formation of hypergranulation tissue which may begin to occur 6-8 weeks post-operatively, but typically the use of rescue medications should be delayed, if possible, for at least 10-12 weeks following the surgical date. This is considered standard of care, as it allows the patient the chance to heal without adjunct medication. The date and time of rescue medication administration as well as the name and regimen of the rescue medication will be recorded in RedCAP. Follow-up after the application of the rescue medication will occur every 6 weeks or until healed, per our surgical standard of care.

For patients receiving rescue medication, the POSAS observer scale total score (primary outcome), POSAS patient scale total score (secondary outcome), and ratio of scar size to initial defect size (secondary outcome) will be recorded at the patient's follow-up visit within 6 weeks of administering the rescue medication, or at a subsequent follow-up visit when the wound is fully healed. (Note that it is not possible to administer the POSAS instrument, a scar assessment tool, if the wound is not completely healed).

As described in Section 9.3, a modified intention-to-treat analysis will be used, in which all patients who have been assessed for the primary study endpoint will be analyzed according to their randomized treatment group.

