8 STUDY ASSESSMENTS AND PROCEDURES

8.1 EFFICACY ASSESSMENTS

The authors will conduct a comparative two-arm study investigating outcomes of second intention healing versus porcine xenograft placement of post-operative Mohs surgery or excision wound defects.

This will be a randomized evaluator blinded study with a prior power analysis. Basic demographic data will be obtained including date of birth, sex, and race. Medical record number will be retained to obtain phone number or address for patient call back should patient not show for their follow-up appointments.

Surgical defects 8 mm in diameter or larger on the lower extremities will be eligible for enrollment. Only patients with one wound will be eligible for enrollment. Primary intention (also known as linear layered) repair is not feasible in many patients with defects on the foot, ankle, or distal extremity as these are sites under high tension and poor circulation. Patients with small post-op defects many also opt not to be sutured via primary intention to avoid physical activity restrictions due to the increased risk of wound dehiscence. When closed via primary intention, a 0.8cm defect results in a scar of greater than or equal to 2.4cm.

Patients will be randomized to either receive a porcine xenograft or allow the wound to granulate via second intention. If primary/linear repair is not an acceptable option, the standard of care at Northwell is to allow the wound to heal on its own via second intention post-operatively. Due to recently published retrospective studies, there is a suggestion that porcine xenografts may be a feasible alternative to second intent healing. Currently, it is the surgeon's (and patient's) choice, after a discussion of risks and benefits of each modality, what is done.

Prior to intervention the defect size will be measured in terms of length and width using a sterile ruler.

After procedure completion wound care instruction will include daily dressing changes and application of petroleum jelly using a cotton tipped applicator to the wound daily until it is healed.

Weekly questionnaires will be given to the patients by phone or email follow-up until 12 weeks postsurgery.

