The mode of treatment for participants will remain consistent throughout the 3-month period, as both methods are reliable for this type of defect. It is not general practice to place a xenograft on a wound healing by second intention or to remove a xenograft after one has been placed to switch to second intention. Should there be any complications, a modified intention to treat principle, described in Section 9, will be adhered to.

The scars for both study groups will be measured at a single follow up visit after 3 months ± 1 month, and two blinded investigators will then assess the scar at this time. The blinded evaluators will be other MDs not involved in the study who are working in the dermatology department. The Principle Investigator will speak with the physician to outline what needs to be recorded for each patient. The validated physician observer scar assessment instrument (POSAS) will be used for this purpose. Scar size will consist of a length x width measurement using a ruler.

The research team consists of one physician who will perform all of the surgical procedures, which will remove bias in technique.>

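### Infection and bleeding are still counted only to the 3-month visit, although rescued patients' scar outcomes can be taken at later visits

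*Combined protocol and SAP*

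**What the plan says.** **Safety endpoints (sections 3 and 9.4.4).** Infection comes from a chart review done once the 3-month visit is complete. It asks whether the patient "visited the dermatologist between the date of surgery and 3-month office visit and if infection was diagnosed". Bleeding is asked in each weekly questionnaire and again at the 3-month visit, and "The number and percentage of patients who experienced bleeding at any time during the 3-month follow-up period will be reported". Section 8.1 ends the questionnaires at week 12 ("Weekly questionnaires will be given to the patients by phone or email follow-up until 12 weeks postsurgery") and places the visit loosely in time: scars are "measured at a single follow up visit after 3 months ± 1 month". Each endpoint is then compared between arms as a plain proportion in the Safety Population, using Fisher's exact test.

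**Rescued wounds (sections 6.5.1 and 9.3).** Rescue typically "should be delayed, if possible, for at least 10-12 weeks following the surgical date". After that, "Follow-up after the application of the rescue medication will occur every 6 weeks or until healed, per our surgical standard of care". For these patients both POSAS totals and the scar-to-defect ratio are taken at a visit within 6 weeks of rescue, or at a later one once the wound has healed. Section 9.3 adds to the mITT Population those who needed rescue and "had the primary endpoint assessed at a follow-up visit when the wound had completely healed".

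**General adverse events (section 8.3.4).** Non-serious events are recorded until 7 days, and serious events until 30 days, after participation ends.

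**The concern.** The revision listed at the front of the protocol changed sections 6.5.1 and 9.3 and left the safety endpoints alone. A patient rescued near the end of the planned follow-up can therefore contribute a late scar score to efficacy, while an infection or bleed between the 3-month visit and that score falls outside the infection and bleeding counts. The same patient is still in the safety denominator, because the Safety Population is everyone who receives the randomized intervention.

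This need not be neutral between arms. Section 2.2 expects the xenograft to shorten healing and reduce complications. If healing does differ, the slower arm has more rescued wounds under observation after the cut-off, and more of its late events are left out. Depending on which arm that is, either a late benefit or a late harm of the xenograft goes uncounted.

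A separate and simpler point affects all patients. Because the chart review ends at a visit that can move by a month either way, patients are observed for infection over unequal times, and a plain proportion takes no account of that.

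**Working it through.** The plan states no length in weeks for the safety window, so there is no figure of its own to reproduce. The inputs are the stated windows, 25 patients per arm (section 9.2), the 1.6% complication rate (section 8.3.2) and the infection rate of under 1% (section 2.3.1).

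**1. When the 3-month visit can fall.** One month = 365.25 / 12 / 7 = 4.35 weeks.
- Earliest, 2 months: 8.7 weeks.
- Nominal, 3 months: 13.0 weeks.
- Latest, 4 months: 17.4 weeks.

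The infection look-back therefore varies by a factor of 17.4 / 8.7 = 2. The last planned bleeding question is at week 12 or at the visit, whichever is later, so between week 12 and week 17.4.

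**2. When post-rescue visits fall.** With rescue at weeks 10 to 12:
- first visit: 10 + 6 to 12 + 6 = weeks 16 to 18;
- second visit: 10 + 12 to 12 + 12 = weeks 22 to 24.

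**3. Distance from the close of the safety endpoints, in weeks.**

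| Reference point | First post-rescue visit | Second post-rescue visit |
|---|---|---|
| Earliest 3-month visit (8.7) | 7.3 to 9.3 after | 13.3 to 15.3 after |
| Last questionnaire (12.0) | 4 to 6 after | 10 to 12 after |
| Nominal 3-month visit (13.0) | 3.0 to 5.0 after | 9.0 to 11.0 after |
| Latest 3-month visit (17.4) | 1.4 before to 0.6 after | 4.6 to 6.6 after |

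The first post-rescue visit is clearly later than a nominal 3-month visit but about level with one at month 4. The second is later than any allowed visit. Section 6.5.1 also permits rescue once hypergranulation forms, which may begin at 6 to 8 weeks. The first visit is then at weeks 12 to 14, so the gap is smaller or absent.

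**4. Whether another planned analysis picks these events up.** Section 8.3.4 may record them. The final comparison in section 9.4.4 covers infection, bleeding and week-1 pain only. A between-arm comparison of serious adverse events is written only for the interim analysis (section 9.4.6), and section 9.4.8 rules out individual listings. A late infection or bleed can thus be on file with no specified place in the final report.

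**5. Size.**
- Expected complications at the stated rate: 50 × 0.016 = 0.8. Expected infections at under 1%: fewer than 50 × 0.01 = 0.5.
- The documents give no rescue rate and no late complication rate. Assume that 5% to 20% of wounds are still open at the close and that 1.6% to 10% of those have a late event. The omitted events are then between 50 × 0.05 × 0.016 = 0.04 and 50 × 0.20 × 0.10 = 1.0.
- Fisher's exact test at 25 per arm, two-sided, k events against 0: p = 2 × C(25,k) / C(50,k). For k = 5, 2 × 53,130 / 2,118,760 = 0.0502. For k = 6, 2 × 177,100 / 15,890,700 = 0.022. If one arm has no events, the other needs six.

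**The case against.** The strongest reply is that a 3-month complication proportion is a legitimate endpoint, applied by the same rule in both arms, and that late events are not lost because section 8.3.4 and section 4.1 require them to be recorded. Few rescues are expected, and nothing ties the timing of the visit to treatment arm, so the variable look-back mainly adds noise. All of this stands. It limits the size of the point but does not close the gap: recording an event is not the same as tabulating it by arm, and section 9.4.4 gives these events no place.

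It could also be said that the 3-month visit simply moves for rescued patients and takes the safety window with it. Section 9.3 does not read that way. It adds patients assessed at a post-rescue visit as a group beyond those who attend the 3-month visit.

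Four stronger readings are tempting and should not be drawn.
- A reader might infer that bleeding closes at week 12. It does not, because it is asked again at the 3-month visit, which can be as late as week 17.4.
- A reader might infer that all unhealed wounds are followed past 3 months. Extended follow-up is written only for rescued wounds.
- A reader might take the time to the next visit as open-wound time. It is only an upper limit, since section 6.5.1 allows for healing by the first post-rescue visit.
- A reader might infer that the cut-off hides a significant difference. With 0.04 to 1.0 omitted events on the assumed rates, and six against none needed, that is not shown.

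**Conclusion.** The mismatch is real and modest. Sections 6.5.1 and 9.3 carry the scar outcomes of rescued patients past the 3-month visit, while sections 3 and 9.4.4 stop infection and bleeding there. Events in the interval may be recorded but have no planned final comparison or summary by arm, and more of them would be omitted in the arm that heals more slowly. The infection look-back also varies twofold, from about 8.7 to 17.4 weeks, with no bias between arms shown.

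The consequence is probably small. It rests on few rescues, as the protocol expects, on a 1.6% complication rate that the protocol gives for dermatologic surgery in general, and on the assumed ranges above. What would be gained is a complete descriptive account of infection and bleeding. When under one complication is expected in the whole trial, leaving out even one changes the reported rates visibly. The primary endpoint and the sample size are not affected.

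**What to change.** In sections 3 and 9.4.4:

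1. **Infection.** Compare arms over one fixed window from surgery for every treated patient, with the chart review run to a fixed date. The end of the allowed visit window, 4 months, is one option.
2. **Bleeding.** Keep the comparison to the 3-month visit as the main analysis. A 4-month bleeding window for everyone would need new patient contacts: a patient seen at month 2 has none planned after week 12, about 17.4 − 12 = 5.4 weeks short.
3. **After rescue.** At the post-rescue visits already planned, ask the same bleeding question and review the chart for infection.
4. **Reporting.** Show these later events by arm on a separate descriptive line, with time observed. Do not pool them into the Fisher comparison: following only slow healers for longer makes exposure depend on an outcome that treatment may change.

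The cost is some wording in the plan and case report form, one extra line in the safety table, and a later chart check for patients whose visit falls early. Care and rescue are unchanged.
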